Obesity is a chronic, heterogeneous complex disease that has reached epidemic proportions. Recently, we identified an abnormal postprandial satiety obesity (APS-OB) phenotype characterized by accelerated gastric emptying, an abnormal postprandial sensation of fullness and reduced satiety hormones such as GLP1 and PYY. In a recent randomized-clinical trial in type 2 Diabetes[1], we showed that ileo-colonic delivery of conjugated bile acids (IC-CBAS) improves glycemia and increases the release of satiety hormones. Elevated fecal Biliary Acids (BA) were also associated to weight loss. However, the specific effect of IC-CBAS in APS-OB is unknown.

Hypothesis:

We hypothesize that IC-CBAS will stimulate enteroendocrine L cell (EEC) secretion of satiety hormones [Glucagon Like peptide 1 (GLP-1), Peptide Tyrosine Tyrosine 3-36 (PYY₃₋₃₆), fibroblast growth factor 19 (FGF-19), oxyntomodulin (OXM)], in the ileum and colon, inducing weight loss and restoring normal satiety in patients with APS-OB.

Aim:

To study the effect of IC-CBAS on EEC function, satiety hormones, microbiota, and body weight in patients with APS-OB phenotype.

Study design:

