Height, weight, blood pressure, heart and respiratory rates, waist and hip ratio, waist circumference, and temperature.
- Baseline and follow-up characteristics studies:
- Methods of metabolic studies:
 - o Body composition will be measured by DEXA (dual energy x-ray absorptiometry).
 - o Resting energy expenditure was assessed by indirect calorimetry with a ventilated hood (Parvo Medics, Sandy, UT).

- Gastric emptying (GE) of solids by scintigraphy [9] [8, 11] Images will be acquired at 0, 30, 60, 90, 120 and 240 minutes following the normal clinical gastric emptying testing protocol without a push meal.
- Satiation will be measured by *ad-libitum* meal to measure total caloric intake and macronutrient distribution in the chosen food. Satiation will be reported in calories consumed at fullness (satiation) [8] [11].
- Appetite sensations by visual analog score fasting and every 30 minutes after the standard meal for GE and the Satiation test up to 2 hours [8, 11].
- Blood samples: The fasting blood samples will be collected during the gastric emptying meal and stored at -70° C freezer. We will analyze plasma glucose, insulin, C-peptide, GLP-1, PYY₃₋₃₆, OXM, FGF-19, 7- α -C4, Adiponectin, Leptin, CCK, Pancreatic Polypeptide (PP), serum bile acids, short chain fatty acids, amino acids[2, 8]. Samples collection, handling, and storage: Samples will be collected after an overnight fast (of at least 8 hours) in the morning. Plasma will be preserved following standard guidelines and protein degradation inhibitors, kallikrein and DPP-IV inhibitors will be added to preserve the samples. Samples will be stored at -80°C in the PI's laboratory. Plasma hormones and proteomics by radioimmunoassay and/or mass spectrometry measured fasting, postprandial, and every 30 minutes for 6 hours. The primary endpoint being the peak postprandial level (test should be done simultaneously to GE).
- Blood DNA for genome wide association studies (GWAS). These samples will be stored for future research.
- Stool samples: One random stool will be collected at baseline and after treatment for fecal bile acids, short chains fatty acids and microbiome.
- Participants with childbearing potential will undergo a pregnancy test.
- Self-administered questionnaires assessing affect, physical activity levels, attitudes, body image, diet, and eating behavior; details of each questionnaire are provided below.

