- Participants will meet with the study team (either in person at the CRTU or virtually) approximately 30 days after visit 2. The study team will assess adverse events, medication compliance, and perform a new medication dispensation (if visit is virtual the medication will be shipped to the participant's preferred address).

- **Visit 4: Study Team visit**

Participants will meet with the study team (either in person at the CRTU or virtually) approximately 30 days after visit 3. The study team will assess adverse events, medication compliance, and perform a new medication dispensation (if visit is virtual the medication will be shipped to the participant's preferred address).

- **Visit 5: Colonoscopy #2**

- Visit 5 will only be completed in the first 6 patients of each group who are willing to consent to both colonoscopy visits.
 - Participants will receive a bowel prep (Movi-prep) during visit 5 and follow standard colonoscopy preparation guides. The next day, after an overnight fasting, a colonoscopy with terminal ileum intubation will be performed. The colonoscopy will be done in the GI clinical or research unit and will be supported by sedation based on patients' characteristics (i.e., conscious sedation vs. anesthesia supported sedation). During the procedure, 8 biopsies will be obtained from the ilium, right and left colon.

- **Visit 6 – Exit Phenotyping**

- Visit 6 will occur within 7 days of Visit 3. Phenotyping will be performed as at the baseline phenotyping visit including the questionnaires performed in screening visit.

Primary Endpoint:

The primary endpoint is EEC function measured through satiety hormones' (GLP-1 & PYY AUC and absolute plasma value curves) comparison between intervention and placebo groups at day 90 in APS-OB phenotype participants.

Secondary Endpoint:

Evaluation of obesity phenotypes through gastric emptying T_{1/2} for solids, satiety sensation with a visual analogue scale (VAS), fullness (VAS), hunger (VAS), desire to eat (VAS), appetite overall score (VAS), ad-libitum buffet meal food intake (kcal), microbial changes, behavioral questionnaires, energy expenditure, and body weight in APS-OB phenotype participants intervened with IC-CBAS, compared to placebo.

Statistical Analysis:

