The primary analysis will compare AUC values between treatment and placebo groups after 90 days of IC-CBAS. Based on the previous study by Calderon et al.[1], we calculated a sample size of 36 subjects. They reported GLP-1 AUC significant difference between intervention and placebo group of 3223 mg/dl. We aim to detect a mean difference in AUC of 3223mg/dl and utilized their IQR to calculate a standard deviation of 3125mg/dl. To have 80% power to detect a difference of 3223mg/dl with a two-sample t-test would require 12 subjects per group. In order to allow for up to 30% dropout, we will enroll 36 subjects total. The effect on weight loss will be evaluated using analysis of covariance (ANCOVA) models, with relative weight loss as the dependent variable, adjusting for gastric emptying (T_{1/2}, min) and gender. Any power lost on degrees of freedom spent on covariate parameter estimation should be more than reclaimed by reduced error variation. For the rest of the endpoints we will compare the data on gastric emptying, satiation parameters, appetite scores, body composition, energy expenditure, GI hormones, bile acids and microbiota between intervention vs. placebo, using the same ANCOVA model. Transformations will be employed as needed for heavily skewed distributions. All treatment effect estimates will be reported with 95% confidence intervals.

POTENTIAL PITFALLS AND PRECAUTIONS TAKEN:

Potential pitfalls of minor significance in this study are:

- **Selection bias** - Participants willing to participate will likely be more motivated to lose weight than the general population. Randomization, double blind will avoid any selection bias;
- **Potential for type II error** - The sample sizes have been based on appropriate statistical power with allowance for drop out. Estimates of variation have been thoroughly characterized in the prior literature from our lab; and other internal and external studies for weight loss at 12 weeks.
- **Feasibility** - We have identified a cohort of people in our community who have obesity, abnormal satiety phenotype, and are willing to participate. We have the experience to successfully recruit 36 participants for the study.

Human Studies Aspects

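### Microbiota is assigned the weight-loss ANCOVA with no microbiota variable, baseline covariate or multiplicity rule, so taxon-level results would have uncontrolled error

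*Combined protocol and SAP*

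**What the plan says.** The Aim names microbiota: "To study the effect of IC-CBAS on EEC function, satiety hormones, microbiota, and body weight in patients with APS-OB phenotype". The Secondary Endpoint section lists "microbial changes, behavioral questionnaires, energy expenditure, and body weight in APS-OB phenotype participants", without saying which microbial quantity is meant. Under Visit 1, the stool-sample item reads "One random stool will be collected at baseline and after treatment for fecal bile acids, short chains fatty acids and microbiome", so a baseline and a post-treatment sample should exist for each completer.

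The Statistical Analysis section introduces the model for weight: "The effect on weight loss will be evaluated using analysis of covariance (ANCOVA) models, with relative weight loss as the dependent variable", adjusted for T1/2 and gender. The remaining endpoints, including "energy expenditure, GI hormones, bile acids and microbiota between intervention vs. placebo, using the same ANCOVA model", are sent to that model. The one flexibility offered is "Transformations will be employed as needed for heavily skewed distributions". Estimates are to be given with 95% confidence intervals.

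The documents name no taxonomic level, diversity index, normalisation, log-ratio or count model, or community-level test. They contain no multiplicity or false-discovery rule, and the baseline value of the outcome is not among the covariates.

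**The concern.** Relative weight loss is one number per participant. A stool microbiome profile is usually many taxa per participant, often expressed as shares that sum to 100%, with many zeros. A univariate ANCOVA can be applied to such data in two ways: to each taxon in turn, or to a summary index. The plan does not choose. The first route multiplies tests with no error control. The second leaves the index to be picked after the data are seen.

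Shares add a separate problem. Because they sum to a constant, a real change in one large taxon moves the shares of all the others even if their absolute amounts are unchanged. The transformation clause addresses skewness and does not remove this constraint.

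The study drug is a bile acid released in the ileum and colon, and the Background describes colonic bacteria transforming bile acids. Taxon findings would therefore be read as mechanism and carried into the larger trials that this study is meant to inform.

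**Working it through.** **The plan's own figure.** There is none for microbiota. The only inputs taken from the plan are the 0.05 level (Study design, in the weight calculation), the two covariates, and the arm sizes: 12 per group required, and 36 enrolled at 1:1, i.e. 18 per group. Number of taxa, between-person variation, share of the changing taxon and size of the change are assumptions.

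**Step 1: multiplicity.** With m independent taxa, none truly affected, each tested at 0.05, the expected number of false positives is 0.05m and P(at least one) = 1 − 0.95^m.

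| Taxa m | Expected false positives | P(at least one) |
|---|---|---|
| 10 | 0.5 | 40% |
| 20 | 1 | 64% |
| 50 | 2.5 | 92% |
| 100 | 5 | 99.4% |

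**Step 2: closure arithmetic.** If a taxon with share s changes f-fold in absolute amount and nothing else changes, every other share is multiplied by 1/(1 − s + s·f).

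- s = 20%, f = 2: 1/1.2 = 0.833, a 17% fall.
- s = 20%, f = 4: 1/1.6 = 0.625, a 38% fall.
- s = 30%, f = 4: 1/1.9 = 0.526, a 47% fall.

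A true fall in the large taxon produces artificial rises instead.

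**Step 3: does the shift become false findings at this sample size?** Simulation, 600 runs per setting: one ANCOVA per taxon on treatment, T1/2 and sex; 12 or 18 per arm; 20, 50 or 100 taxa; log-normal abundances with SD 1 on the log scale. One taxon with a 20-30% share truly rises f-fold and all others are unchanged. Percentage of unchanged taxa called significant at 5%:

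| True change | Relative abundance or its log |
|---|---|
| none | 4-5%, both directions equally |
| 2-fold | 5-7% |
| 4-fold | 8-17% (relative abundance); 13-28% (log), nearly all decreases |

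A plain log, the usual answer to skewness, makes the closure error worse.

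**Step 4: does the remedy work?** With a centred-log-ratio transform, the error per unchanged taxon is 4.9-5.7% in every setting. Adding Benjamini-Hochberg at 5% brings the chance of any false call among unchanged taxa to about 3-10%, against 62-99% with the transform alone. Benjamini-Hochberg without the log-ratio transform still leaves 8-36% (relative abundance) or 30-73% (log) at a 4-fold change. Both parts are needed.

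The simulation contains no zeros and no baseline adjustment, so it does not test those parts of the fix.

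**The case against.** The strongest reply is that the documents never say taxa, or shares of taxa, will be tested. If the intended measure is one pre-specified scalar, such as a diversity index, ANCOVA is suitable and neither problem arises. That is correct, and it locates the main defect: an undefined variable tied to a one-outcome model. It does not remove the point, because no index is named and one chosen after the data are seen is also uncontrolled.

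A reader might infer three stronger things.

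- *That the trial will almost certainly report false taxa.* This depends on the number tested. At a coarse taxonomic level with 10 or 20 taxa the chance is 40% or 64%, and the documents do not exclude that. Independence is assumed too, which sits uneasily with shares that are tied together.
- *That the analysis will produce artificial decreases in any event.* Closure distorts only when a sizeable taxon truly changes, and the direction depends on whether that taxon rises or falls. At a doubling, shares shift by 17% but the false-call rate stays at 5-7% against a nominal 5%.
- *That the trial's main conclusion is at risk.* The primary comparison concerns GLP-1 and PYY and does not involve microbiota.

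It is also fair that this is a proof-of-concept trial with many secondary endpoints, for which the plan promises intervals and states no significance rule. That lowers the stakes and argues against any confirmatory microbiota test. It does not supply a definition or error control.

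**Conclusion.** The point holds as a gap in specification. The plan assigns an aim and secondary endpoint to a model built for a single outcome and leaves open the variable, the baseline adjustment and the multiplicity rule. Under taxon-by-taxon use, the chance of a false positive ranges from 40% (10 taxa) to 99.4% (100 taxa), given independence and no true effect. Closure is a conditional, second-order problem: negligible at a 2-fold change in a large taxon, material at about 4-fold (8-28% of unchanged taxa called significant), under the simulated variation and shares of 20-30%. The plan should be changed because the correction is cheap, but the fault is confined to a secondary endpoint.

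**What to change.** In the Statistical Analysis section, remove microbiota from the list sharing the weight-loss ANCOVA and specify the following before unblinding.

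1. **One scalar summary**, such as Shannon diversity, analysed by ANCOVA with its baseline value, T1/2 and gender as covariates.
2. **Single-taxon comparisons**, labelled exploratory: a stated prevalence filter, a stated zero replacement, a centred-log-ratio transform, adjustment for the baseline value, and Benjamini-Hochberg control at a stated rate (for example 5%).
3. **Optionally, a community-level test**, with treatment labels permuted within the randomisation strata, also labelled exploratory.

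No new samples, visits or participants are needed, since baseline and post-treatment stool are already planned. The cost is plan wording, slightly more analysis work and fewer nominally significant taxa.

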APPENDIX A: QUESTIONNAIRES

Bowel Disease Questionnaire

In the past 12 months, have you experienced the following?

QUESTION	YES	NO
1. 2 or less than 2 bowel movements/week		
2. Excessive straining or sensation of incomplete evacuation of stool on more than 25% of occasions		
3. Lumpy stools on more than 25% of occasions		
At least 3 months of continuous or recurrent symptoms of:		
4. Abdominal pain or discomfort relieved by defecation		
5. Abdominal pain or discomfort associated with a change in stool frequency		
6. Abdominal pain or discomfort associated with a change in stool consistency		
7. More than 3 bowel movements per day		
8. Loose watery stools		
9. Bloating		
10. Swallowing difficulties		
11. Upper abdominal pain after meals more than once a month		
12. Abdominal bloating after meals		
13. Nausea regularly more than once a month		
14. Vomiting regularly more than once a month		
15. Heartburn regularly more than once a week		
16. Acid reflux regularly more than once a week		

Sign _____ Date _____

The Hospital Anxiety and Depression Questionnaire

Please read each item and circle the reply which best describes how you have been feeling during the past week. Don't devote too much time to your responses; your immediate reaction will probably be more accurate than a long thought out response.

1. I feel tense or 'wound up' :
 - Most of the time
 - A lot of the time
 - Occasionally
 - Not at all
2. I still enjoy the things I used to enjoy :
 - Definitely as much
 - Not quite so much
 - Only a little
 - Hardly at all
3. I get a frightened feeling, as if something awful is about to happen :
 - Very definitely and quite badly
 - Yes, but not too badly
 - A little, but it doesn't worry me
 - Not at all
4. I can laugh and see the funny side of things :
 - As much as I always could
 - Not quite so much now
 - Definitely not so much now
 - Not at all
5. Worrying thoughts go through my mind :
 - A great deal of the time
 - A lot of the time
 - From time to time
 - Only occasionally
6. I feel cheerful :
 - Not at all
 - Not often
 - Sometimes
 - Most of the time
7. I can sit at ease and feel relaxed :
 - Definitely
 - Usually
 - Not often
 - Not at all
8. I feel as if I am slowed down :
 - Nearly all the time
 - Very often
 - Sometimes
 - Not at all
9. I get a frightened feeling, like 'butterflies in the stomach' :
 - Not at all
 - Occasionally
 - Quite often
 - Very often
10. I have lost interest in my appearance :
 - Definitely
 - I don't take as much care as I should
 - I may not take quite as much care
 - I take just as much care as ever
11. I feel restless as if I have to be on the move :
 - Very much indeed
 - Quite a lot
 - Not very much
 - Not at all
12. I look forward with enjoyment to things :
 - As much as I ever did
 - Rather less than I used to
 - Definitely less than I used to
 - Hardly at all
13. I get sudden feelings of panic :
 - Very often indeed
 - Quite often
 - Not very often
 - Not at all
14. I can enjoy a good book or TV program :
 - Often
 - Sometimes
 - Not often
 - Very seldom

Sign _____ Date _____

Bristol Stool Scale

Stool form	Appearance	Type
Separate hard lumps, like nuts (hard to pass). Result of slow transit		1
Sausage-shaped but lumpy		2
Like a sausage but with cracks on its surface		3
Like a sausage or snake – smooth and soft		4
Soft blobs with clear cut edges (easy to pass)		5
Fluffy pieces with ragged edges, a mushy stool		6
Watery, no solid pieces. Result of very fast transit		7

Circle the form which best describes your normal bowel movements.

Ease of Passage:

1. Manual disimpaction required
2. Enema or suppository required to initiate bowel movement
3. Some straining necessary to pass bowel movement
4. Easy normal passage of stool without straining
5. Urgent need to pass bowel movement spontaneously; **no** abdominal pain or discomfort present
6. Urgent need to pass bowel movement spontaneously; abdominal pain or cramping present
7. Incontinent of bowel movements

Physical Activity Stages of Change Questionnaire

For each of the questions below, please check Yes or No. Please be sure to follow the instructions carefully.

Physical activity or exercise includes activities such as walking briskly, jogging, bicycling, swimming or any other activity where the exertion is at least as hard as these activities. Your heart rate and breathing should increase.

	NO	YES
1. I am currently physically active		
2. I intend to become more physically active in the next 6 months		

For activity to be regular, it must add up to a total of 30 minutes or more per day, and be done at least 5 days per week. For example, you could take one 30 minute walk, or take three 10 minute walks each day.

	NO	YES
3. I currently engage in regular physical activity		
4. I have been regularly physically active for the past 6 months		

Sign: _____ Date: _____

Eating Patterns Questionnaire

— 15	
1. During the past six months, did you often eat within any two-hour period what most people would regard as an unusually large amount of food?
 
 Yes  No → SKIP TO QUESTION 5
		
— 16	
2. During the times when you ate this way, did you often feel you couldn't stop eating or control what or how much you were eating?
 
 Yes  No → SKIP TO QUESTION 5
		
— 17	
3. During the past six months, how often, on average, did you have times when you ate this way – that is, large amounts of food plus the feeling that your eating was out of control (there may have been some weeks when it was not present – just average those in).
 
 
   Less than one day a week  One day a week  Two or three days a week 	  Four to five times a week  Nearly every day 	
 
	 Less than one day a week  One day a week  Two or three days a week	 Four to five times a week  Nearly every day
 Less than one day a week  One day a week  Two or three days a week	 Four to five times a week  Nearly every day		
— 18	
4. Did you usually have any of the following experiences during these occasions?
 
a. Eating much more rapidly than usual?  Yes  No
		
— 19	
b. Eating until you felt uncomfortably full?  Yes  No
		
— 20	
c. Eating large amounts of food when you didn't feel physically hungry?  Yes  No
		
— 21	
d. Eating alone because you were embarrassed by how much you were eating?  Yes  No
		
— 22	
e. Feeling disgusted with yourself, depressed, or feeling very guilty after overeating?  Yes  No
		
— 23	
5. In general, during the past six months, how upset were you by overeating (eating more than you think is best for you)?
 
 
   Not at all  Slightly  Moderately 	  Greatly  Extremely 	
 
	 Not at all  Slightly  Moderately	 Greatly  Extremely
 Not at all  Slightly  Moderately	 Greatly  Extremely		
— 24	
6. In general, during the past six months, how upset were you by the feeling that you couldn't stop eating or control what or how much you were eating?
 
 
   Not at all  Slightly  Moderately 	  Greatly  Extremely 	
 
	 Not at all  Slightly  Moderately	 Greatly  Extremely
 Not at all  Slightly  Moderately	 Greatly  Extremely		

7. During the past six months, how important has your weight or shape been, in how you feel about or evaluate yourself as a person – as compared to other aspects of your life, such as how you do at work as a parent, or how you get along with other people?

— 25

- 1 Weight and shape were **not very important**
- 2 Weight and shape **played a part** in how you felt about yourself
- 3 Weight and shape **were among the main things** that affected how you felt about yourself
- 4 Weight and shape **were the most important things** that affected how you felt about yourself

8. During the past **three** months, did you ever make yourself vomit in order to avoid gaining weight after binge eating?

— 26

— 27

- 1 Yes →
- 0 No

How often, **on average**, was that?

- 1 Less than one day a week
- 2 One day a week
- 3 Two or three days a week
- 4 Four to five times a week
- 5 More than five times a week

9. During the past **three** months, did you ever take more than twice the recommended dose of laxatives in order to avoid gaining weight after binge eating?

— 27

— 28

- 1 Yes →
- 0 No

How often, **on average**, was that?

- 1 Less than one day a week
- 2 One day a week
- 3 Two or three days a week
- 4 Four to five times a week
- 5 More than five times a week

10. During the past three months, did you ever take more than twice the recommended dose of diuretics (water pills) in order to avoid gaining weight after binge eating?

— 29

— 30

- 1 Yes →
- 0 No

How often, **on average**, was that?

- 1 Less than one day a week
- 2 One day a week
- 3 Two or three days a week
- 4 Four to five times a week
- 5 More than five times a week

11. During the past three months, did you ever fast – not eat anything at all for at least 24 hours --in order to avoid gaining weight after binge eating?

— 31

— 32

1 Yes —————→
0 No

How often, **on average**, was that?
1 Less than one day a week
2 One day a week
3 Two or three days a week
4 Four to five times a week
5 Nearly every day

12. During the past three months, did you ever exercise for more than an hour **specifically** in order to avoid gaining weight after binge eating?

— 33

— 34

1 Yes —————→
0 No

How often, **on average**, was that?
1 Less than one day a week
2 One day a week
3 Two or three days a week
4 Four to five times a week
5 More than five times a week

13. During the past three months, did you ever take more than twice the recommended dose of a diet pill in order to avoid gaining weight after binge eating?

— 35

— 36

1 Yes —————→
0 No

How often, **on average**, was that?
1 Less than one day a week
2 One day a week
3 Two or three days a week
4 Four to five times a week
5 More than five times a week

Sign _____ Date _____

Multi-dimensional Body-Self Relations Questionnaire (MBSRQ)

On a scale of 1 (very dissatisfied) to 5 (very satisfied) please indicate how satisfied you are with each of the following areas or aspects of your body:

	Very dissatisfied	Mostly dissatisfied	Neither satisfied nor dissatisfied	Mostly satisfied	Very satisfied
1. Face (facial features, complexion)	1 	2 	3 	4 	5 
2. Hair (color, thickness, texture)	1 	2 	3 	4 	5 
3. Lower torso (buttocks, hips, thighs, legs)	1 	2 	3 	4 	5 
4. Mid torso (waist, stomach)	1 	2 	3 	4 	5 
5. Upper torso (chest or breasts, shoulders, arms)	1 	2 	3 	4 	5 
6. Muscle tone	1 	2 	3 	4 	5 
7. Weight	1 	2 	3 	4 	5 
8. Height	1 	2 	3 	4 	5 
9. Overall appearance	1 	2 	3 	4 	5 

Sign _____ Date _____

**EFFECT OF ILEOCOLIC-RELEASE CONJUGATED BILE
ACID ON SATIETY AND ENTERO-ENDOCRINE CELL
FUNCTION IN PATIENTS WITH OBESITY AND ABNORMAL
SATIETY PHENOTYPE**

IRB #

Food Diary

Diet: Normal Diet, Baseline

Dates: _____ to _____

**[name] [name],
Principal Investigator**

[name]

[REDACTED]

FOOD INTAKE DIARY – Baseline*Complete every day. Return to Mayo Clinic on visit 1.*

- Please record your food, medications and beverage intake every day, in the table below.
- Record everything you eat! For example, if you add sugar to your coffee or eat a bite-sized candy, you still have to record these items.
- Make sure to include amount of food consumed. (example: 8 oz coffee, 2 tbsp peanut butter, 1 cup white rice, 12 oz steak with 2 tbsp steak sauce, 2 slices wheat bread with 1 slice american cheese, 3 pieces of salami, and 1 tsp mayonnaise.)
- If eating at a restaurant or eating prepackaged food include name of restaurant/food brand, item ordered/eaten, and amount consumed.
- If eating at a restaurant or eating prepackaged food also include calories per serving and servings consumed.

Day 1

Date _____

Meal	Intake	Notes
Breakfast		
AM Snack (if any)		
Lunch		
PM Snack (if any)		
Dinner		
Other		

Participant's Signature: _____

Date: _____

Day 2

Date _____

Meal	Intake	Notes
Breakfast		
AM Snack (if any)		
Lunch		
PM Snack (if any)		
Dinner		
Other		

Participant's Signature: _____

Date: _____

Day 3

Date _____

Meal	Intake	Notes
Breakfast		
AM Snack (if any)		
Lunch		
PM Snack (if any)		
Dinner		
Other		

Participant's Signature: _____

Date: _____

Day 4

Date _____

Meal	Intake	Notes
Breakfast		
AM Snack (if any)		
Lunch		
PM Snack (if any)		
Dinner		
Other		

Participant's Signature: _____

Date: _____

Day 5

Date _____

Meal	Intake	Notes
Breakfast		
AM Snack (if any)		
Lunch		
PM Snack (if any)		
Dinner		
Other		

Participant's Signature: _____

Date: _____

Day 6

Date _____

Meal	Intake	Notes
Breakfast		
AM Snack (if any)		
Lunch		
PM Snack (if any)		
Dinner		
Other		

Participant's Signature: _____

Date: _____

Day 7

Date _____

Meal	Intake	Notes
Breakfast		
AM Snack (if any)		
Lunch		
PM Snack (if any)		
Dinner		
Other		

Participant's Signature: _____

Date: _____

AUDIT-C Questionnaire

Patient Name _____ Date of Visit _____

1. How often do you have a drink containing alcohol?

- a. Never
- b. Monthly or less
- c. 2-4 times a month
- d. 2-3 times a week
- e. 4 or more times a week

2. How many standard drinks containing alcohol do you have on a typical day?

- a. 0
- b. 1 or 2
- c. 3 or 4
- d. 5 or 6
- e. 7 to 9
- f. 10 or more

3. How often do you have six or more drinks on one occasion?

- a. Never
- b. Less than monthly
- c. Monthly
- d. Weekly
- e. Daily or almost daily

AUDIT-C is available for use in the public domain.

Weight Management Questionnaire

**TO BE SCANNED
QUESTIONNAIRE**

Instructions: It is very important that you fill out this questionnaire completely. A complete questionnaire helps your nutrition team provide the best care for you. Return the completed form to your registered dietitian (RD) or Endocrinology provider at the time of your appointment.

Patient Information

Mayo Clinic Number	Patient Name (First, Middle, Last)	Date Today (Month DD, YYYY)
Living Situation		
 Alone  With others, describe _____		
Employment		
 Full-time  Part-time  Disabled  Retired  Unemployed  Homemaker		

Weight History

How old were you when you first became overweight?

10-20 years old 20-30 years old 30-40 years old 40-60 years old greater than 60 years old

What is the most you have ever weighed?

_____ pounds How old were you? _____

Can you identify significant life events when you gained weight (i.e., pregnancy, menopause, new job, etc.)?

No

Yes

If yes, what events? _____

What is the least you have weighed since 18 years of age?

_____ pounds How old were you? _____

How long did you maintain that weight? _____ months or _____ years

What did you weigh (if not applicable, leave blank):

Graduating high school _____ pounds

On union/wedding day _____ pounds Age _____ years old

One year ago _____ pounds

Three months ago _____ pounds

Today _____ pounds

Weight-Related Complications

Indicate which of the following weight-related conditions you are experiencing.

- Diabetes or elevated blood glucose
- Heartburn/reflux (GERD)/indigestion
- High blood pressure (hypertension)
- High cholesterol (hyperlipidemia)/Coronary artery disease (CAD)
- Obstructive sleep apnea (OSA) or difficulty sleeping
- Joint pain
- Asthma
- Other, specify _____

Family

Instructions: Indicate members of your family who are or have been overweight and whether they have experienced any of the problems listed below.

	Overweight			High Blood Pressure	Diabetes or High Blood Glucose	High Cholesterol	Heart Disease
	Less than 20 pounds	20 to 50 pounds	More than 50 pounds				
Mother							
Father							
Brother(s)							
Sister(s)							

Past and Current Weight Control Measures

Instructions: Complete the table below about various methods you have used to control your weight.

Methods used to control weight	Previously?		Currently?		Pounds Lost	Pounds Regained
	Yes	No	Yes	No		
Dieting on your own? If yes, briefly explain.						
"Commercial" weight loss plan/system (i.e., Weight Watchers, Overeaters Anonymous, Atkins, other, etc.) If yes, briefly explain.						
Surgeries (weight loss). If yes, specify date and type of surgery.						
Have you ever used or engaged in the following to control your weight: Caffeine, "energy" drinks or pills "Water" pills Vomiting Laxatives Prolonged fasting (greater than 24 hours) Other						
Have you ever been prescribed medication to help control your weight (i.e., orlistat [Alli, Xenical], sibutramine [Meridia], phentermine, other)? If yes, briefly explain.						

Nutritional Supplements

Do you take nutritional supplements?

No

Yes If yes, describe below.

Multi-vitamin/mineral

Calcium

_____ milligrams (mg) _____ times/day

Vitamin D

_____ international units (IU) _____ times/day

Calcium plus vitamin D (combined supplement)

_____ milligrams (mg) of calcium _____ international units (IU) of vitamin D _____ times/day

Other (herbs, extracts, protein powder/bars, fish oil) _____

Physical Activity

Do you regularly exercise (i.e., go for walks, go jogging, go to a health club, go swimming)?

No

Yes If yes, briefly describe what you do for exercise, how often, and for how long. _____

Do you often stay active doing other things (i.e., your job, yard work, farming, etc.)?

No

Yes If yes, briefly describe what you do, how often, and for how long. _____

What do you feel are the primary factors limiting you from doing more physical activity (check all that apply)?

Pain (joint, nerve) during or after physical activity

Too tired/fatigued

Do not enjoy physical activity/boring

Not sure what type of activity to do

Do not have enough time

Not sure how to safely be active

Self-conscious while being physically active

Other. Briefly describe. _____

Eating Patterns and Preparation

Have you ever talked with a registered dietitian (RD)?

No

Yes If yes, when and for what reason? _____

How many meals do you usually eat each day?

On work days _____ On days off _____

Do you snack (eat between main meals)?

No

Yes How often? _____ times/day

What time of day? _____

What do you usually snack on? _____

Who prepares most of the food you eat?

You Spouse Family Member Other, describe _____

Do you eat out at restaurants?

No

Yes Breakfast _____ times/week Lunch _____ times/week Dinner _____ times/week

Eating Patterns and Preparation

Do you ever feel your eating is out of control or that you eat an excessive amount of food at one time?

No

Yes If yes, describe how often this occurs and what types of situations result in this behavior? _____

Do you feel something other than what you eat and drink explains your difficulty controlling your weight (i.e., slow metabolism)?

No

Yes If yes, explain _____

List the types and amounts of foods and beverages you usually eat for each of the meals/snacks listed below.

Breakfast:  Yes  No	Morning Snack:  Yes  No
Lunch:  Yes  No	Afternoon Snack:  Yes  No
Evening Meal:  Yes  No	Evening Snack:  Yes  No

Fill in the blanks below. About how often do you consume the various foods and beverages listed during a usual week?

Sugar, Honey, Jelly/Jam, Syrup _____ times per week	Milk (8 ounces) (Check one)  Whole  2%  1%  Skim _____ times per week
Butter, Margarine, Added Oil _____ times per week	Yogurt (6-8 ounces) _____ times per week
Cake, Pie, Ice Cream, Candy _____ times per week	Cheese, types _____ times per week
Beef, Chicken, Pork, Lamb, Veal (4 ounces, about the size of a deck of cards) _____ times per week	Vegetables (½ cup serving) _____ times per week
Fish (4 ounces, about the size of a deck of cards) _____ times per week	Beer, Wine, Liquor (1 serving) _____ times per week
Fruit (1 serving) _____ times per week	Carbonated Beverages/Soft Drinks  Diet  Regular _____ times per week
Fruit Juices (6-8 ounces) _____ times per week	
Breads _____ times per week	
Other Starches (rice, noodles, potatoes) _____ times per week	

Food Guide

Grains	Vegetables	Fruits	Milk	Meat and Beans
6 oz. per day	2 ½ cups per day	2 cups per day	3 Cups per day	5 ½ oz. per day

Dosimetry per administration

Model: Adult				Organ/Wt (organ doses are in mGy)														
RAM	Activity per administration (mCi)	Activity per administration (MBq)	Number of administrations	Testes	Ovaries	Breast	RBM	Lung	Thyroid	Bone	Colon	Stomach	Bladder	Liver	Esoph	Other SI	Remainder	
				0.1	0.1	0.05	0.12	0.12	0.05	0.01	0.12	0.12	0.05	0.05	0.05	0.025	0.025	
Tc-99m Non-Absorbable Markers (solids, oral)	0.5	18.5	1	0.02	0.48	0.01	0.09	0.02	0.00	0.09	1.85	1.09	0.13	0.08	0.01	1.13	0.07	
In-111 Non-Absorbable Markers (liquid, oral)	0.05	1.85	1	0.06	0.78	0.01	0.18	0.01	0.00	0.06	2.83	0.22	0.22	0.06	0.01	0.93	0.07	
Total				0	1	0	0	0	0	0	5	1	0	0	0	2	0	
				Remainder organ Mass (g)	adrenal	brain	kidney	muscle	pancreas	SI	spleen	thymus	uterus		Weighted Average			
Tc-99m Non-Absorbable Markers (solids, oral)	Organ dose	0.07	0.00	0.12	0.07	0.20				0.14	0.01	0.30			0.07			
In-111 Non-Absorbable Markers (liquid, oral)	Organ dose	0.04		0.08	0.08	0.08				0.06		0.31			0.07			

E (mSv): **0.97**

Additional Comments:
Ref. - <insert reference>
In-111 non absorb. markers (liquid): Ref. ICRP 53, pg. 250.
Tc-99m non absorb. Markers (solids): Ref. ICRP 80, table 3.13.2.
Remainder are mass weighted average of named remainder organs (ICRP 60).

0 Minute

Directions: Answer each question about how you are feeling by drawing a vertical mark (|) at the appropriate point through the horizontal line of each question.

How hungry do you feel?

I am not
hungry at all

I have never
been more hungry

How satisfied do you feel?

I am
completely
empty

I cannot eat
another bite

How full do you feel?

Not at all full

Totally full

How much do you think you can eat?

Nothing at all

A lot

Would you like to eat something sweet?

Yes, very much

No, not at all

Would you like to eat something salty?

Yes, very much

No, not at all

Would you like to eat something savoury?

Yes, very much

No, not at all

Would you like to eat something fatty?

Yes, very much

No, not at all

30 Minute

Directions: Answer each question about how you are feeling by drawing a vertical mark (|) at the appropriate point through the horizontal line of each question.

How hungry do you feel?

I am not
hungry at all

I have never
been more hungry

How satisfied do you feel?

I am
completely
empty

I cannot eat
another bite

How full do you feel?

Not at all full

Totally full

How much do you think you can eat?

Nothing at all

A lot

